13.3 Handling of Missing, Unused, and Spurious Data

Only subjects for whom data are available will be included in the statistical analysis. Missing values will be neither replaced nor estimated in the primary analysis. A sensitivity analysis, in which all missing data will be considered as treatment failures will be performed for the FAS to assess the influence of missing data on the primary efficacy results. In addition, a worst-case analysis will also be performed, in which any subjects in the CELSTAT treatment group with missing primary efficacy data will be categorized as treatment failures, and any subjects in the Surgicel treatment group with missing primary efficacy data will be categorized as treatment successes.

13.4 Methods of Analysis

13.4.1 Primary Outcome Measures

The primary efficacy analysis will be carried out on the PPS. The analysis using the FAS will be used as a supportive analysis.

The primary efficacy parameter is defined as follows: The primary endpoint is set to success if hemostasis is achieved at 5 minutes after the treatment application and is maintained until surgical closure. If hemostasis is not achieved at 5 minutes, if additional hemostatic treatment other than study device is required, or if intraoperative rebleeding occurs, the primary endpoint will be set to “treatment failure”.

The primary effectiveness endpoint will be investigated by a 2-sided test for non-inferiority using the confidence-interval (CI) approach to compare the CELSTAT group to the Surgicel group. A non-inferiority margin of 10% (the largest clinically acceptable difference) will be used; thus, if the lower bound of the 2-sided 95% CI (based on normal approximation) around the difference in proportions (CELSTAT group - Surgicel group) is greater than -10% in the final analysis, CELSTAT will be declared non-inferior to Surgicel.

The specific hypotheses of the risk difference to be tested are as follows:

$$H_0: P_{\text{CELSTAT}} - P_{\text{Surgicel}} \leq -\delta$$

$$H_1: P_{\text{CELSTAT}} - P_{\text{Surgicel}} > -\delta$$

where

P_{CELSTAT} = the proportion (%) of subjects achieving hemostasis by 5 minutes in the CELSTAT group,

P_{Surgicel} = the proportion (%) of subjects achieving hemostasis by 5 minutes in the Surgicel group, and

δ = the non-inferiority margin of 10%.

Additionally, if the lower bound of the 2-sided 95% CI is larger than zero, superiority of CELSTAT versus Surgicel will be claimed.

The null hypothesis will be tested against the alternative using logistic regression, taking into account the following covariates: study center, surgery type (cardiothoracic, general or vascular) and initial bleeding severity (mild or moderate).

The primary safety analysis, of the difference in proportion of subjects rebleeding from the TBS requiring surgical re-exploration during the subject's study participation, will be performed using the same logistic regression model described for the primary efficacy endpoint.

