9.4 Outcome Measures

9.4.1 Primary Outcome Measures

9.4.1.1 Effectiveness

The primary effectiveness outcome measure is the proportion of subjects with hemostasis achieved at the TBS at 5 minutes after the start of application of the study device.

Hemostasis is defined as Grade 0 bleeding (no bleeding; see [Table 2](#) in Section 9.2) at the TBS after application of the randomized treatment, with no subsequent rebleeding at the TBS through surgical closure and no additional hemostatic treatment of another type after application of the randomized treatment.

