12.2 Assessment of Effectiveness

For statistical analysis, the observation period includes the 10 minutes after start of application of the study device to the TBS.

The surgeon (who will be trained on the Bleeding Severity Scale [see [Table 2](#)] prior to study participation) will perform all intraoperative hemostasis assessments of the TBS, including identifying the TBS.

The severity of bleeding (Grade 1 or 2; see [Table 2](#)) at the TBS at the time of its identification (and prior to start of study device application) will be recorded.

A stop watch will be started at the start of device application. After application, the device is to be held firmly in place for at least 30 seconds. The occurrence and time of occurrence (or absence) of hemostasis (ie, Grade 0 bleeding; see [Table 2](#)) at the TBS will be recorded after the start of device application. Recurrence of bleeding, time of recurrence, and subsequent time of hemostasis will also be recorded, if applicable.

If hemostasis appears to be achieved early, but rebleeding occurs during the 10-minute assessment period, more of the randomized product may be applied and the hemostasis assessment will continue. TTH is defined as the time from the start of application of the study device until the first timepoint at which hemostasis at the TBS was observed and after which no rebleeding from the TBS occurred during the 10-minute observation period (subsequent intraoperative rebleeding will be considered a treatment failure).

In addition, any intraoperative rebleeding from the TBS after the initial 10-minute assessment period and prior to surgical closure will be recorded.

Treatment failure is defined as any of the following:

- Hemostasis not being achieved within 10 minutes
- Occurrence of bleeding complications during the 10-minute hemostasis assessment period requiring hemostatic measures other than application of the randomized study treatment
- Intraoperative rebleeding after the 10-minute hemostasis assessment period that is treated with the randomized study treatment or with any other hemostatic measures

The responsible study personnel will also record the following surgical, TBS, device administration, and hemostasis/rebleeding information during the peri- and intraoperative periods:

- Date of surgery
- Time of start and end of surgery (first skin incision/last skin suture)
- Surgery type (cardiothoracic, general, vascular)
- Indication for surgery and surgical procedure performed

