- Anatomical location of TBS
- Tissue type (soft tissue, parenchymal or vascular)
- Type of conventional hemostatic measures at the TBS before randomization
- Time of completion of conventional hemostatic methods at TBS
- Identity (CELSTAT or Surgicel) and lot number of the applied study product
- Number of sheets of the study product applied to the TBS
- Number of sheets of the study product left in situ at surgical closure
- Reason, if study product removed prior to surgical closure
- Use of additional hemostatic treatment (yes/no) other than the study product at the TBS (ie, if hemostasis was not obtained during the 10-minute observation period, or if hemostasis was achieved but intraoperative rebleeding occurred); time of use (ie, number of minutes after clock start or after the 10 minute observation period), and type of additional hemostatic treatment

- Use of anticoagulation and reversal during surgery, including:
 - Whether any anticoagulation was used (yes/no)
 - Anticoagulant used, start and end times of administration and dose administered for each dose administered
 - Reversal agent used (if any), start and end times of administration and dose administered for each dose administered
 - Whether cardiopulmonary bypass was used (yes/no) and, if yes, start and end times of bypass
- Timepoint(s) of intraoperative rebleeding, if any, at the TBS after the 10-minute observation period (to also be documented as an AE [see Section 12.3.2.4])
- Intraoperative complications including death (to be documented as AEs)

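### The primary-endpoint rule is worded differently in 9.4.1.1, 12.2 and 13.4.1, so a dry site given another hemostat as a precaution has two possible scores and is not reliably recorded

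*Protocol*

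**What the plan says.** Three sections of the protocol bear on the same endpoint.

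- **9.4.1.1** defines hemostasis as Grade 0 bleeding with no later rebleeding through closure and "no additional hemostatic treatment of another type after application of the randomized treatment". There is no condition on why the other treatment was given.
- **13.4.1** gives its own rule. "The primary endpoint is set to success if hemostasis is achieved at 5 minutes after the treatment application and is maintained until surgical closure". Failure follows if hemostasis is not achieved at 5 minutes, if there is intraoperative rebleeding, or "if additional hemostatic treatment other than study device is required".
- **12.2** uses hemostasis as Grade 0 only: "The occurrence and time of occurrence (or absence) of hemostasis (ie, Grade 0 bleeding; see [Table 2](#)) at the TBS will be recorded". Its treatment-failure list ties other measures to need or to a rebleed: "Occurrence of bleeding complications during the 10-minute hemostasis assessment period requiring hemostatic measures other than application of the randomized study treatment", and "Intraoperative rebleeding after the 10-minute hemostasis assessment period that is treated with the randomized study treatment or with any other hemostatic measures".

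The data item in 12.2 is "Use of additional hemostatic treatment (yes/no) other than the study product at the TBS", with time and type. A parenthesis qualifies it: "ie, if hemostasis was not obtained during the 10-minute observation period, or if hemostasis was achieved but intraoperative rebleeding occurred".

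Section 9.8.1.3 asks that only the randomized product be relied on at the TBS, but only for the 10-minute observation period. The endpoint runs to surgical closure. Under 9.6.1 and 9.6.2 the surgeon learns the assignment before the device is applied, and under 12.2 the surgeon makes all intraoperative hemostasis assessments.

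**The concern.** Consider a TBS that is Grade 0 by 5 minutes, does not rebleed, and is covered with another hemostat before closure as a precaution. Under 9.4.1.1 this is not hemostasis. On the wording of 13.4.1 nothing was *required* and nothing rebled, so the subject can be scored a success. The primary endpoint then turns on which section the analyst follows.

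This matters for two reasons. The decision to reinforce a dry site, and the judgement whether reinforcement was required, both lie with a surgeon who knows the arm. The extra product may also prevent a rebleed that would have counted as a failure, so a success may be credited to the study device that belongs partly to another product. If such use differs between arms, the comparison shifts, and the data item as worded may not show by how much.

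**Working it through.** **1. The passages side by side, for the dry site with a precautionary hemostat**

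| Section | Condition on other treatment | Score |
|---|---|---|
| 9.4.1.1 | none may be given | not hemostasis |
| 13.4.1, hemostasis read as Grade 0 (as in 12.2) | failure if required | success |
| 13.4.1, hemostasis read as the 9.4.1.1 term | none may be given | not a success |
| 12.2 failure list | complication requiring it, or treated rebleed | not listed as failure |
| 12.2 data item | recorded for non-hemostasis or rebleeding | outside the parenthesis |

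The text does not settle which reading of 13.4.1 applies.

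**2. The plan's sample size**

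Inputs from 13.1: 121 evaluable per group, margin 10 points, 1-sided 2.5%, power 80%, 5% loss to the per-protocol set. The assumed success rates are redacted, so 121 cannot be strictly reproduced. The unpooled formula n = (1.960 + 0.842)² × [pC(1−pC) + pS(1−pS)] / (pC − pS + 0.10)² gives 122 for 90% on CELSTAT and 89% on Surgicel, so 121 is plausible. 121/0.95 = 127.4, rounded up to 128; the next multiple of 3 is 129, as stated. One subject is 1/121 = 0.83 points.

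**3. Effect on the chance of declaring non-inferiority**

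Assumptions: true success by the 9.4.1.1 rule is 89% on Surgicel (the pilot rate in 7.3.2) and 79% on CELSTAT, exactly at the margin. A share q of subjects fails 9.4.1.1 only through precautionary use but is scored a success. The protocol gives no value for q, so a range is shown; 2% of 121 is about 2 subjects and 5% about 6.

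Non-inferiority is declared if d − 1.96 × √[p̂C(1−p̂C)/121 + p̂S(1−p̂S)/121] > −0.10, where d = p̂C − p̂S. The probability is summed exactly over two independent binomials with n = 121. The scored rates are 0.79 + q and 0.89 (CELSTAT only), 0.79 + q and 0.89 + q (both arms), or 0.79 and 0.89 + q (Surgicel only). Covariates are ignored.

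| q | CELSTAT only | Both arms equally | Surgicel only |
|---|---|---|---|
| 0% | 2.8% | 2.8% | 2.8% |
| 2% | 7.0% | 2.9% | 1.0% |
| 5% | 21.8% | 3.1% | 0.1% |

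For CELSTAT-only use at q = 3% the figure is 10.6%. It is 9.1% if the Surgicel rate is 85%, and 13.1% if it is 93%, with CELSTAT 10 points lower in each case.

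**4. How few subjects can change a conclusion**

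With 109/121 = 90.1% scored as success in each arm, d = 0 and the standard error is √(2 × 0.9008 × 0.0992/121) = 0.0384. The lower bound is −1.96 × 0.0384 = −7.5%. Rescoring CELSTAT subjects as failures gives:

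- 1 subject (108/121): −8.5%
- 2 subjects (107/121): −9.5% (−0.0945)
- 3 subjects (106/121): d = −2.48 points, standard error 0.0404, lower bound −10.4%

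At this result, three subjects reverse the conclusion.

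**The case against.** The strongest reply is that there is no conflict. Hemostasis is a defined term in 9.4.1.1, and 8.1 refers to that section for the detailed definition. Success in 13.4.1 depends on hemostasis, so the condition on other treatment comes with it. The failure sentence does not say *only*. This stands as a possible reading, and a reader who inferred that 13.4.1 scores the case outright as a success would go beyond the text. It does not remove the ambiguity: 13.4.1 sets out its own definition, its clause on required treatment would then be redundant, and 12.2 uses Grade 0 alone.

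The 12.2 failure list is built around 10 minutes, not the 5-minute endpoint, so its silence is weak evidence on primary scoring. That is accepted.

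A reader might also infer that precautionary use is not recorded at all. The documents do not support that. The yes/no item exists, with type and time, and a site could answer yes. Section 12.1 asks for all therapies, though it exempts routine perioperative treatment, and 17.3 requires full source data verification. What remains is that capture depends on how each site reads the parenthesis.

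Within the first 10 minutes, 9.8.1.3 already directs reliance on the randomized product. The gap is mainly from minute 10 to closure.

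Finally, a reader might infer a bias towards non-inferiority. That needs more precautionary use on CELSTAT sites, for which the protocol offers no evidence. Equal use leaves the error rate almost unchanged, and use on Surgicel sites lowers it.

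**Conclusion.** The point holds as an inconsistency in the primary-endpoint rule combined with unreliable capture of the event on which the readings differ. It is not an established bias. Its frequency and direction are unknown. At the margin, with 79% against 89% and 121 per arm, the chance of a false non-inferiority claim at q = 5% ranges from 0.1% to 21.8% depending on the arm, against 2.8% with no such cases. The upper figure assumes that every case is in the CELSTAT arm. With 109/121 successes in each arm, three rescored subjects are enough to cross the margin. The rates are assumptions, because the protocol's own are redacted.

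A statistical analysis plan, not shown here, could choose between the readings. It could not recover data that sites were not clearly asked to record, so the data item needs attention in the protocol and the eCRF.

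**What to change.** 1. In 13.4.1, base failure on use instead of need: additional hemostatic treatment other than the study device *is used at the TBS between start of device application and surgical closure*. This matches 9.4.1.1.
2. Align 12.2, both its description of hemostasis and its failure list, with the same rule.
3. In the 12.2 data item, delete the restricting parenthesis, so that any non-study hemostatic treatment at the TBS up to closure is recorded with its time, type and reason.
4. Add a sensitivity analysis that scores precautionary use on a dry site as success.

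The cost is protocol wording, one eCRF field and one extra analysis. These changes concern scoring and recording only, not how bleeding is treated. There are two drawbacks. Success rates may fall slightly. The endpoint also still depends on a discretionary act by an unblinded surgeon, because reinforcing a dry site now counts as a failure. The recorded reason and the sensitivity analysis do not remove that dependence, but they make it visible.

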7.3.2 Prior CELSTAT Clinical Investigation

The sponsor conducted a pilot clinical study (Study 621101) to evaluate the safety and effectiveness of CELSTAT (brand name Traumastem in the study report) as an adjunct to hemostasis for tissue bleeding in subjects undergoing open cardiac, intraabdominal (including retroperitoneal) or pelvic surgery as compared to Surgicel. This was a prospective, randomized, positive-controlled, subject-blinded, multicenter study.

In eligible subjects, the study treatment was applied at the TBS after conventional surgical hemostasis was completed. The number and size of layers of device used was at the discretion of the surgeon. The investigational device did not need to be removed and could be left in situ.

All 82 subjects enrolled achieved hemostasis at the primary TBS within 10 minutes. At 5 minutes after the start of device application hemostasis was achieved in 51 of 55 subjects (93%) in the CELSTAT group and in 24 of 27 subjects (89%) in the Surgicel group. Median time to hemostasis (TTH) in the CELSTAT group was 117 seconds, compared with 158 seconds in the Surgicel group.

The proportion of subjects with any adverse event (AE)/adverse device effect (ADE) was similar for the CELSTAT and Surgicel groups, with 74.5% (41/55 subjects) and 74.1% (20/27 subjects), respectively. Only 3 AEs/ADEs (postprocedural hematoma, postprocedural complication, and liver abscess) in the Surgicel group, all occurring in 1 subject, were considered by the investigator to be related to study treatment.

The pilot study defined AEs/ADEs of special interest as any of the following:

- Postoperative rebleeding
- Infection: signs included fever $>100^{\circ}\text{F}$ or $>37.8^{\circ}\text{C}$ after the first 48 hours with malaise and or lethargy
- Hematoma at the surgical site

- Change in coagulation parameters (as noted by change from normal or abnormal without clinical significance, respectively, at baseline to abnormal or abnormal with clinical significance at Day 7 (± 1)/Discharge (Visit 3): prothrombin time, activated partial thromboplastin time, platelet count
- Increased wound healing time (more than 2 weeks) or wound dehiscence
- Foreign body reactions and allergic reactions (to device and material); signs of inflammation or encapsulation
- Embolization (especially vascular surgeries) and associated complications

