9.6 Randomization and Blinding

9.6.1 Randomization

Subjects will be randomly assigned to CELSTAT or Surgicel at a ratio of 1:1. Randomization will be stratified by study center and surgery types (cardiothoracic, general, vascular surgery). It is aimed to achieve a similar distribution of the 3 surgery types in the randomized study population. This will be controlled via an interactive Web-response system (IWRS), [REDACTED] (USA), using dynamic allocation. Within [REDACTED], a capping strategy will be used to ensure equal allocation of randomized subjects across surgical types. On the day of surgery, upon confirmation of preoperative eligibility criteria, a member of the site study staff other than the surgeon will obtain a treatment assignment (CELSTAT or Surgicel) from the IWRS. To keep the surgeon blinded until an eligible TBS has been identified for study treatment, adequate amounts of each study product (CELSTAT and Surgicel) will be taken into the operating room for potential use of one of them as the study treatment.

Immediately after the subject's intraoperative eligibility for study treatment has been confirmed (ie, an eligible TBS with Grade 1 or 2 bleeding has been identified), the assigned treatment will be revealed to the surgeon and the assigned device will be applied to the TBS. Following surgery, the treatment assignment and the actual treatment applied will be entered in the electronic case report form (eCRF) for the subject.

If the subject's eligibility is not confirmed pre- or intraoperatively, the subject's operation will be performed according to hospital standards. The study site designee will enter the date and reason(s) for the subject's exclusion in the eCRF.

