9.6.2 Blinding

This will be a single-blinded study. The subjects undergoing scheduled surgery will be blinded. In addition, the surgeon performing the surgery will remain blinded until an eligible TBS has been identified for study treatment (see Section 9.6.1). Otherwise, investigators, surgery personnel, site study personnel, CRO personnel and sponsor personnel will not be blinded.

[REDACTED]

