13.2 Datasets and Analysis Cohorts

Two types of analyses of effectiveness are planned: analysis of the full analysis set (FAS) and of the PPS. Assessment of safety will be carried out on all subjects treated (safety analysis set).

Full analysis set: The FAS will consist of all subjects who are randomized. Subjects will be analyzed as randomized.

Per-protocol analysis set: The PPS is defined as a subset of the FAS. Subjects will be excluded from the PPS if they:

- Do not meet all inclusion/exclusion criteria
- Are randomized but not treated according to the randomization scheme
- Violate other major study procedures that may influence the study results

Safety analysis set: The safety analysis set will consist of all subjects who are treated with CELSTAT or Surgicel. Subjects will be analyzed as treated.

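### Superiority would be claimed from the per-protocol confidence interval, with the full analysis set only supportive, so the claim need not hold in the subjects as randomised

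*Protocol*

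**What the plan says.** Section 13.4.1 of the protocol opens with the analysis sets: "The primary efficacy analysis will be carried out on the PPS", and "The analysis using the FAS will be used as a supportive analysis". Section 13.1 also places the primary analysis on the PPS. Section 13.4.1 then defines one two-sided 95% confidence interval for the CELSTAT minus Surgicel difference. It uses that interval for non-inferiority against the 10-point margin and adds: "Additionally, if the lower bound of the 2-sided 95% CI is larger than zero, superiority of CELSTAT versus Surgicel will be claimed".

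Section 13.2 defines the sets. For the full set, "The FAS will consist of all subjects who are randomized", analysed as randomised. The PPS drops subjects who fail eligibility, who were not treated as assigned, or who committed other major procedural violations that might affect the results. The last criterion is a matter of judgement.

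On blinding, section 9.6.1 says that once an eligible target bleeding site (TBS) is confirmed, "the assigned treatment will be revealed to the surgeon and the assigned device will be applied to the TBS". Section 12.2 says the surgeon "will perform all intraoperative hemostasis assessments of the TBS". Section 9.6.2 says that, apart from the subject and the surgeon up to that moment, "investigators, surgery personnel, site study personnel, CRO personnel and sponsor personnel will not be blinded".

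**The concern.** Non-inferiority and superiority call for different analysis sets. In a non-inferiority test, including protocol violators can pull the arms together and make success easier, so a PPS analysis is a reasonable primary choice. In a superiority test the danger runs the other way: removing subjects after randomisation can create or enlarge a difference, and the as-randomised comparison is the protection.

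Here one interval serves both decisions, and it comes from the PPS. Those who could influence an exclusion may know both the arm and the outcome, so exclusions can depend on both. A difference whose interval includes zero among the randomised subjects could become a superiority claim in a trial that section 9.1 calls pivotal. The protocol gives no rule by which a contrary FAS result would block it.

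**Working it through.** **1. Which interval drives the claim.** The superiority sentence names no analysis set. It refers to the interval defined just before it, in a section that opens by placing the primary analysis on the PPS. The only other FAS analyses are in section 13.3 (missing counted as failure, and a worst case by arm). They address missing data and do not govern the claim. The PPS reading therefore follows from the text.

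**2. The plan's own figures.** The assumed success rates are redacted, so the 121 evaluable subjects per group cannot be reproduced exactly. Whole-percent pairs that come close (Surgicel/CELSTAT) include 89/90 (122 per group), 83/86 (122) and 86/88 (124). The next step does reproduce: 121/0.95 = 127.4, rounded up to 128, and 129 is the next number divisible by the three surgery types.

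**3. Illustrative counts (an assumption).** The pilot study in section 7.3.2 reports hemostasis at 5 minutes in "51 of 55 subjects (93%) in the CELSTAT group and in 24 of 27 subjects (89%) in the Surgicel group". Scaled to 129 per arm:

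- CELSTAT: 129 × 51/55 = 119.6, taken as 120 successes and 9 failures
- Surgicel: 129 × 24/27 = 114.7, taken as 115 successes and 14 failures

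**4. Interval.** d ± 1.96 × √[p₁(1−p₁)/n₁ + p₂(1−p₂)/n₂]. This is the unadjusted normal approximation; section 13.4.1 also specifies a logistic regression with covariates, so the exact switching points are illustrative.

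| Scenario | CELSTAT | Surgicel | Difference, points (95% CI) | Superiority claimed? |
|---|---|---|---|---|
| All randomised | 120/129 | 115/129 | +3.9 (-3.1 to 10.8) | No |
| 3 CELSTAT failures excluded | 120/126 | 115/129 | +6.1 (-0.4 to 12.6) | No |
| 4 CELSTAT failures excluded | 120/125 | 115/129 | +6.9 (0.5 to 13.2) | Yes |
| 4 CELSTAT and 1 Surgicel failure excluded | 120/125 | 115/128 | +6.2 (-0.1 to 12.4) | No |
| 4 failures excluded per arm | 120/125 | 115/125 | +4.0 (-1.9 to 9.9) | No |

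For the third row: p₁ = 0.9600, p₂ = 0.8915, SE = 0.0325, lower bound = 0.0685 − 1.96 × 0.0325 = 0.0048.

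Four exclusions are 4/129 = 3.1% of the arm, inside the 5% loss planned in section 13.1, though part of that 5% may be subjects with no eligible TBS. They are also 4/9 = 44% of the CELSTAT failures.

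**5. Range.** With CELSTAT held at 120/129, the number of excluded CELSTAT failures (and no other exclusions) at which the lower bound passes zero is:

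| Surgicel successes of 129 | 111 | 112 | 113 | 114 | 115 | 116 | 117 | 118 | 119 | 120 |
|---|---|---|---|---|---|---|---|---|---|---|
| Exclusions needed | 1 | 2 | 3 | 3 | 4 | 5 | 5 | 6 | 7 | 7 |

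In every column the interval on all 129 per arm includes zero. With equal arms (120 each), 7 of the 9 CELSTAT failures would have to go.

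**6. False-claim rate.** Simulation with 129 per arm, equal true rates and 400,000 runs, excluding at random a fixed share of CELSTAT failures only:

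| True rate in both arms | No selective exclusion | A quarter excluded (mean subjects) | Half excluded (mean subjects) |
|---|---|---|---|
| 85% | 2.6% | 12% (4.8) | 41% (9.7) |
| 89% | 2.6% | 10% (3.5) | 32% (7.1) |
| 93% | 2.7% | 8% (2.3) | 22% (4.5) |

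The nominal one-sided rate is 2.5%. The one-arm exclusion pattern is assumed in order to show sensitivity; nothing in the protocol predicts it.

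**The case against.** The strongest reply is that the scenario is extreme. Four exclusions sound few, but they are nearly half of the CELSTAT failures, with no CELSTAT success and no Surgicel subject removed; adding a single Surgicel failure reverses the result. The protocol also closes an obvious route for losing failures, since section 13.4.1 scores additional hemostatic treatment and intraoperative rebleeding as treatment failure. Superiority is an add-on: the sample size is for non-inferiority, and power for superiority at the pilot rates is only about 0.18 to 0.20. A PPS comparison is still between randomised arms, and the superiority sentence does not itself name the PPS.

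These points limit the size of the risk. They do not remove the fault. The risk depends on unbalanced exclusions, and the protocol has no rule that protects the claim if they occur: one PPS criterion is open to judgement, most staff are unblinded, and the FAS has no say in the decision. Nor is this a detail left for the SAP. The protocol already fixes the set, the interval, the threshold and the claim, so an SAP that based superiority on the FAS would depart from it.

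Two points about the remedy also deserve weight. Leaving out subjects with no eligible TBS is safe only if the assignment stays concealed from the surgeon in the operating room, because another staff member already holds it. And section 11.1 counts the intraoperative criterion as part of eligibility for randomisation, whereas section 9.6.1 obtains the assignment before that criterion is checked. The two sections should be brought into line.

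**Conclusion.** The concern holds. As written, superiority is claimed automatically from the PPS interval, and the as-randomised result can neither confirm nor block it. At counts assumed from the pilot rates, four excluded CELSTAT failures turn +3.9 (-3.1 to 10.8) into +6.9 (0.5 to 13.2); over the range examined the number needed runs from one to seven. If a quarter of CELSTAT failures were excluded, the false-claim rate would rise from about 2.6% to between 8% and 12%.

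These figures rest on assumed counts, an unadjusted interval and exclusions confined to one arm. With balanced exclusions the claim does not appear. The use of the PPS for non-inferiority is not faulted, and that conclusion is unaffected. The change should be made, but the trial's main inference does not depend on it.

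**What to change.** In section 13.4.1, replace the superiority sentence with wording such as:

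> If non-inferiority is shown in the PPS, superiority will be claimed only if the lower bound of the 2-sided 95% CI in the modified FAS, analysed as randomised, is greater than 0. The PPS superiority result is supportive.

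In section 13.2, define the modified FAS as all randomised subjects with an eligible TBS confirmed before the assignment is revealed to the surgeon. A separate label is needed because the present FAS is everyone randomised, and section 9.6.1 obtains the assignment before intraoperative eligibility is known; some FAS members may therefore have no TBS and no outcome. These subjects are identified while the surgeon is still blinded, so leaving them out should not bias the comparison provided concealment holds. The missing-as-failure and worst-case analyses already planned in section 13.3 can be applied to the modified FAS to test any superiority claim against missing outcomes.

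The cost is wording in two sections, with no change to sample size or conduct. A superiority claim may become slightly harder to reach.
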